6.2.2 Process for Determining Inclusion in Populations

Inclusion into the ITT and Safety populations will be determined programmatically from the eCRF data. Inclusion into the CE populations will be determined programmatically from the eCRF data and the manual review conducted by the ERT. The ERT may review subject data to confirm that population criteria are satisfied.

Inclusion into the microITT population will be determined programmatically by incorporating the outcome of the review of the isolates by the ERT. The ERT will determine whether each isolate (baseline and post-baseline) is considered a pathogen based on a review of information from baseline samples including Gram stain results, and local and central laboratory genus and species identification. Inclusion into the ME populations will be determined programmatically.

Review of data, Sponsor determination of evaluability, and final subject population classification will be performed in a blinded manner prior to database lock and unblinding with the exception of those criteria requiring the subject's actual treatment assignment (for

example, the requirement for the subject to have received the correct test article per the randomization assignment). For the criteria requiring the subject's actual treatment assignment, population determination will be completed programmatically.

6.3 Subgroups

Analyses will be conducted (as described in [Section 10](#)) for subgroups defined by the randomization stratification factors: PORT Risk Class (II vs III/IV), receipt of an allowed antibacterial therapy in the 72 hours prior to study treatment (yes vs no), geographic region (Western Europe/North America, Eastern Europe, vs Rest of World). Analyses of Early Clinical Response (in the ITT population) and overall assessment of clinical response at the PTE visit (in the ITT and CE-PTE populations) will also be conducted in the following subgroups: bacteremic subjects, defined as subjects with a positive blood culture at baseline (microITT population), by CURB-65 Score, and subjects meeting the systemic inflammatory response syndrome (SIRS) criteria at baseline. CURB-65 Score is derived from the eCRF data and ranges from 0-5 where 1 point is given for each of the following at baseline: confusion, blood urea nitrogen > 19 mg/dL (urea > 6.8 mmol/L), respiratory rate ≥ 30 breaths/min, systolic blood pressure < 90 mmHg or diastolic blood pressure ≤ 60 mmHg, and age ≥ 65 years. Confusion is defined as altered mental status as recorded on the PORT Risk Class Determination eCRF. SIRS is defined as having 2 or more of the following criteria: temperature $< 36^{\circ}\text{C}$ or $> 38^{\circ}\text{C}$ (oral or oral equivalent), heart rate > 90 bpm, respiratory rate > 20 breaths/min, or WBC count < 4000 cells/mm³ or $> 12,000$ cells/mm³ or $> 10\%$ bands.

Exploratory analyses in other subgroups may also be conducted.

7 CHANGES IN CONDUCT OR PLANNED ANALYSES FROM THE PROTOCOL

The expanded microITT population was added and selected analyses are conducted in this population.

8 OVERALL STATISTICAL CONSIDERATIONS

8.1 General Conventions

The following general comments apply to all statistical analyses and data presentations:

- Summaries will include frequency and percentages for categorical data; frequency and median for ordinal data; and frequency, mean, standard deviation, and median, minimum, and maximum for quantitative data.
- Duration variables will be calculated using the general formula (end date – start date) +1.
- Change from baseline will be calculated for each subject at the specified time point as the value at the specified time point minus the baseline value.
- If the reported value of a clinical laboratory parameter cannot be used in a statistical summary table (eg, a character string is reported for a parameter of the numerical type), a coded value must be appropriately determined and used in the statistical analyses. In general, a value or lower and upper limit of normal range such as ‘< 10’ or ‘≤ 5’ will be treated as ‘10’ or ‘5’ respectively, and a value such as ‘> 100’ will be treated as ‘100.’ However, the actual values as reported in the database will be presented in data listings. Data will be reviewed on an ongoing basis in a blinded manner to assess the frequency of occurrence of laboratory parameters reported as a character string.
- Individual subject listings of all data represented on the eCRFs will be provided to facilitate the investigation of tabulated values and to allow for the clinical review of all efficacy and safety parameters.
- Version 9.3 (or higher) of SAS® statistical software package will be used to provide all summaries, listings, graphs, and statistical analyses.

8.2 Baseline Definition

In general, baseline is defined as the value closest to but prior to the initiation of test article administration. If no test article is received, baseline is defined as the value closest to but prior to randomization.

For pathogen determination, baseline is defined as either Day –1 or 1 (the 24-hour period prior to the administration of the first dose of test article) or if the subject is unable to produce a sputum sample at baseline or the sputum sample does not have an adequate Gram stain, a specimen obtained within 24 hours after the first dose of test article may be used as baseline. If no test article is received, for pathogen determination, Study Day is defined based on date of randomization.

For analyses of vital signs and ECGs, if no value is available prior to the initiation of test article administration, a value within 2 hours after initiation of test article administration can be used as baseline.

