In iv studies in healthy subjects, modest and reversible alanine aminotransferase (ALT) increases were seen most notably with iv doses of 300 mg or greater (3 × higher than the therapeutic dose of 100 mg iv). There were no differences in ALT changes in the Phase 2 study compared to linezolid. Transient increases in heart rate were observed following administration of single and multiple doses of omadacycline, with a dose dependent mean increase of up to 15-20 beats per minute (bpm) compared to placebo for the first 4 hours after dosing. The increases in heart rate were not reported as AEs and not associated with any other cardiac findings. These increases were observed most consistently during the 2 hours immediately post-infusion. Beyond 6 hours after the start of the infusion, heart rate in all subjects, including controls, were comparable. A listing of all Phase 1 AEs is provided in Appendix I of the IB ([Paratek, 2014](#)).

In the Phase 2 study, omadacycline was well-tolerated. The most frequently reported AEs were GI-related occurring in 21 (18.9%) of 111 omadacycline-treated, and 18 (16.7%) of 108 linezolid-treated subjects. Nausea and vomiting were reported in 11 (9.9%) and 5 (4.5%), respectively, of omadacycline-treated subjects primarily during po treatment, compared to 8 (7.4%) and 4 (3.7%), respectively, of linezolid-treated subjects. Premature discontinuation of treatment due to an AE was very infrequent, occurring in 0.9% and 1.9% of omadacycline and linezolid-treated subjects, respectively.

There was no pattern of adverse changes in laboratory safety parameters among subjects treated with omadacycline or linezolid; changes in omadacycline-treated subjects were comparable to those observed with linezolid. In particular, there was no clinical or statistical difference between the treatment groups in ALT values or in other liver function tests (LFTs).

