An increase in mean heart rate was observed, but to a much lesser extent than what was observed in Phase 1 studies. During the first 4 hours following the start of the first infusion of omadacycline there was a mean increase in heart rate from Baseline of 2.5 bpm for omadacycline (range from -20 to 40 bpm), peaking at 4 hours, as compared to a slight decrease of -0.1 bpm effect on heart rate for the linezolid treatment arm (range from -21 to 22 bpm), $p = 0.005$. This effect was transient and no QT prolongation was observed, consistent with the omadacycline thorough corrected QT interval (QTc) and human Ether-à-go-go-Related Gene (hERG) studies. Three subjects treated with omadacycline had AEs of tachycardia; 1 other subject reported palpitations. All 4 of these AEs were mild in intensity, all were assessed as either unrelated or unlikely related to test article, and none resulted in discontinuation of study treatment. Three of these AEs occurred during the first week of treatment; 1 AE occurred 8 days after completing therapy and was associated with a new infection (at a different site).

A Phase 3 cSSSI study enrolled 143 subjects prior to being discontinued due to a change in the Food and Drug Administration (FDA) Guidance for the development of antimicrobials for acute bacterial skin and skin structure infections (ABSSSI). The overall incidence of reported AEs in this study was comparable between the 2 treatment groups. The most commonly reported AEs ($\geq 10\%$ frequency in either treatment group) were nausea (26.5% omadacycline, 26.4% linezolid), headache (23.5% omadacycline, 6.9% linezolid), vomiting (8.8% omadacycline, 15.3% linezolid), diarrhea (4.4% omadacycline, 18.1% linezolid), and dizziness (10.3% omadacycline, 8.3% linezolid). Creatine phosphokinase (CK) elevation was reported in 8.8% of omadacycline-treated subjects compared to 2.8% for linezolid. AEs associated with ALT increases were reported in 4 linezolid-treated subjects (5.6%) compared to 1 omadacycline subject (1.5%). Six linezolid subjects (8.3%) reported rash compared to 1 subject (1.5%) on omadacycline. Four subjects experienced serious adverse events (SAEs) (3 omadacycline and 1 linezolid). The 3 omadacycline SAEs consisted of small bowel obstruction, large left pleural effusion, and worsening depression. The 1 linezolid SAE consisted of worsening right hand cellulitis.

For full details of safety findings in nonclinical and clinical studies, see the IB ([Paratek, 2014](#)).

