11.2 Vital Signs

Blood pressure (systolic and diastolic), respiratory rate, temperature, and pulse/heart rate will be summarized using descriptive statistics at the following time points: prior to each infusion while the subject is on iv treatment, EOT Visit, PTE Visit, and highest and lowest post-baseline value. Heart rate and blood pressure will be summarized for the following additional time points: for the first 3 doses of test article, just prior to the first infusion, within 30 to 90 minutes after the start of the first infusion and 3.5 to 5.5 hours after the start of the first infusion. Descriptive statistics of the change from baseline to each post-baseline time point and the highest and lowest post-baseline value will also be provided. Baseline is defined as the value closest to but prior to the initiation of test article administration. If no value is available prior to the initiation of test article administration, a value within 2 hours after initiation of test article administration.

Post-baseline vital signs will be defined as clinically notable (CN) if they meet the criterion value or both the criterion value and the change from baseline criterion listed in [Table 8](#). The incidence of CN vital signs will be summarized by time point and treatment group, and will be listed and flagged in by-subject listings. The overall post-baseline incidence of CN values for each vital sign parameter, which includes values from unscheduled post-baseline visits, will also be summarized. A listing will also be provided of subjects with a CN vital sign and will list all values for a vital sign noted as CN.

Table 8. Criteria for Treatment Emergent Clinically Notable Vital Signs

Vital Sign Parameter	Flag	Criterion Value	Change from Baseline
Systolic Blood Pressure (mmHg)	High (CH)	≥ 180	Increase of ≥ 20 mmHg
	Low (CL)	≤ 90	Decrease of ≥ 20 mmHg
Diastolic Blood Pressure (mmHg)	High (CH)	≥ 105	Increase of ≥ 15 mmHg
	Low (CL)	≤ 50	Decrease of ≥ 15 mmHg
Heart Rate (bpm)	High (CH)	≥ 120	Increase of ≥ 15 bpm
	Low (CL)	≤ 50	Decrease of ≥ 15 bpm
Temperature (°C)	Low (CL)	<36.0	NA
	High (CH)	>38.0	NA

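### For subjects with no pre-dose reading, the SAP lets a vital sign or ECG taken up to 2 hours after dosing starts serve as baseline, which biases their heart-rate change toward zero

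*Combined protocol and SAP*

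**What the plan says.** The default in SAP 8.2 is sound: "In general, baseline is defined as the value closest to but prior to the initiation of test article administration". An exception follows, with its own trigger: "For analyses of vital signs and ECGs, if no value is available prior to the initiation of test article administration", then "a value within 2 hours after initiation of test article administration can be used as baseline". SAP 11.2 restates it for vital signs: "If no value is available prior to the initiation of test article administration, a value within 2 hours after initiation of test article administration". SAP 11.3 does the same for ECGs. Those two restatements have no main verb and take their meaning from 8.2. SAP 11.3 also says that the central ECG results are the ones analysed.

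Protocol 16.1.2 schedules heart rate and blood pressure around each of the first three doses: just before the first infusion, at 30-90 minutes, and at 3.5-5.5 hours after its start. Protocol 16.1.4.1 schedules ECGs at Screening, within 30 minutes before the first dose, and 30-90 minutes after the first infusion starts.

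Protocol 9.1 describes what omadacycline does to heart rate. In Phase 1 there were transient rises, "with a dose dependent mean increase of up to 15-20 beats per minute (bpm) compared to placebo for the first 4 hours after dosing", and "These increases were observed most consistently during the 2 hours immediately post-infusion". In the Phase 2 skin-infection trial there was a "mean increase in heart rate from Baseline of 2.5 bpm for omadacycline (range from -20 to 40 bpm), peaking at 4 hours", against a change of -0.1 bpm on linezolid. The same section reports no QT prolongation with omadacycline.

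**The concern.** A baseline should be free of the drug. Here the fallback value is taken while a known, early effect of the investigational drug may already be present. The reading most likely to be used is the 30-90 minute one, which is scheduled soon after dosing, when that effect would be looked for. The SAP does not say whether a reading used as baseline also counts as post-baseline.

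At stake, for affected subjects, are the change-from-baseline summaries for heart rate and the heart-rate row of SAP Table 8, which pairs a value of at least 120 bpm with a rise of at least 15 bpm. The bias runs toward showing no change on a safety signal that the protocol itself describes.

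**Working it through.** The plan gives no figure for how often the fallback would be used, so there is nothing to reproduce. The check is of timing, then of one subject, then of the arm.

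**Timing.** The omadacycline infusion runs for 30 to 45 minutes (protocol Table 1, note b).
- For a 30-minute infusion, the 2 hours after infusion run from 0.5 to 2.5 h after the start of dosing.
- The fallback window is 0 to 2 h. The overlap is 2 - 0.5 = 1.5 h, or 2 - 0.75 = 1.25 h for a 45-minute infusion.
- The 30-90 minute reading (0.5-1.5 h) lies wholly inside the fallback window.

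**One subject.** Let the true pre-dose heart rate be b (not recorded), with rises d1 at 30-90 minutes and d2 at 3.5-5.5 hours. If the 30-90 minute reading becomes baseline:
- change at 30-90 minutes is (b + d1) - (b + d1) = 0, or is not defined, instead of d1;
- change at 3.5-5.5 hours is (b + d2) - (b + d1) = d2 - d1 instead of d2;
- a flag that requires the rise is lost when the later value is at least 120, d2 is at least 15, and d2 - d1 is below 15.

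In Phase 2 the mean rise peaked at 4 hours, after the fallback window closes. On average d1 is then smaller than d2, and the masking at the later reading is partial.

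**The arm.** Let f be the share of the omadacycline arm on a post-dose baseline and E the true mean rise. If the whole rise is already in the baseline (the worst case), the arm's mean change falls from E to (1 - f)E, a loss of f x E.
- Arm size: 750 randomized 1:1, so about 375.
- E from Phase 2, net of linezolid: 2.5 - (-0.1) = 2.6 bpm.
- E from Phase 1, upper figure: 15-20 bpm.
- f: **assumed**, 1% to 10%.

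| f (assumed) | Subjects of 375 | Loss at E = 2.6 | Loss at E = 15 | Loss at E = 20 |
|---|---|---|---|---|
| 1% | about 4 | 0.03 bpm | 0.15 bpm | 0.20 bpm |
| 5% | about 19 | 0.13 bpm | 0.75 bpm | 1.0 bpm |
| 10% | about 38 | 0.26 bpm | 1.5 bpm | 2.0 bpm |

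Turned round, a loss of 0.5 bpm needs f = 0.5/2.6 = 19% (about 72 subjects) at the Phase 2 effect. At the Phase 1 figures it needs 0.5/15 = 3.3% to 0.5/20 = 2.5% (about 13 to 9 subjects).

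**How often.** Vital signs and ECG are each due twice before dosing. Inclusion criterion 4 rests on vital signs, the PORT score includes pulse, and exclusion criterion 7 rests on QTcF. A dosed subject without any pre-dose vital sign should be an exception. The ECG is somewhat less protected: since central results are analysed, a pre-dose tracing without a usable central reading could also trigger the rule.

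**The case against.** The strongest reply is that this is a last-resort convention. It operates only when both the Screening and the immediate pre-dose readings are missing, it is specified in advance, and it applies to both arms. Raw heart rate is summarized at every time point and as the highest and lowest post-baseline value, and QTcF is also shown in absolute categories, so a real signal would remain visible. The wording of SAP 11.2 may also allow a clinically notable flag on the criterion value alone. All of this stands, and it is why the point is minor. It does not make a post-dose reading a valid baseline, and rarity means that dropping the rule costs little. For laboratory values SAP 11.4 falls back only on another pre-dose result.

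A reader might go further in three ways that the documents do not support.
- **That the heart-rate effect is masked across the omadacycline arm.** This would need f near 100%, and the trigger condition rules that out in practice.
- **That QTcF change is understated on omadacycline.** Protocol 9.1 reports no QT prolongation, so there is no documented effect to hide.
- **That the distortion is one-sided because moxifloxacin subjects first receive placebo.** For heart rate, the documents describe a rise only with omadacycline. For ECGs the argument fails: active moxifloxacin follows the 30-45 minute placebo infusion and so starts well inside the 2-hour window.

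**Conclusion.** The concern holds for individual subjects and is small for the trial. Where the fallback is used in the omadacycline arm, heart-rate change, and any flag relying on it, is biased toward zero to the extent that the rise has already begun at the reading used. At arm level the worst case is about 0.03-0.26 bpm for an assumed 1-10% of subjects at the Phase 2 effect.

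The Phase 1 figures give 0.15-2.0 bpm over the same range, but they are less relevant here. They are an upper value for a dose-dependent effect, from a program with single iv doses up to 600 mg, whereas this trial gives 100 mg iv, and protocol 9.1 says that the Phase 2 rise was much smaller.

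The result rests on the assumed f, for which the documents give no figure, and on full masking in every affected subject, which overstates the loss. Efficacy analyses and sample size are untouched.

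**What to change.** Delete the 2-hour fallback from SAP 8.2, 11.2 and 11.3. Keep the default already in 8.2, and say explicitly that Screening counts as a pre-dose value. If no pre-dose value exists, set baseline and change from baseline to missing, and keep the post-dose reading in the by-time-point and highest/lowest summaries. State how the Table 8 flag is assigned when the change is missing, which the SAP now leaves open.

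The cost is an edit of three sentences and a handful of subjects leaving the change-from-baseline rows.

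If the sponsor prefers to keep the fallback, the minimum is to report by arm how many subjects use it, to bar a reading used as baseline from also counting as post-baseline, and to repeat the change summaries without those subjects.

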8.3 Handling of Missing Data

Missing data will be handled as outlined below:

- All missing and partial dates for adverse events or for medications received after randomization will be queried for a value. If no value can be obtained, substitutions will be made as detailed in [Appendix 3](#). These substitutions will be used in calculations; however, the actual value recorded on the eCRF will be used in all listings.
- Missing start and stop times for prior and concomitant antibiotics will be queried for a value. If no value can be obtained but the site indicates the antibiotic was received (onset time) prior to the first dose of test article, 00:01 will be used for the onset time. If the site also indicates that the end time was prior to the first dose of test article, 00:01 will be used for end time. The actual value (blank) will be recorded on the eCRF and will be used in the listings.
- Missing times for assessments of CABP symptoms will be queried for a value. If minutes are not available, the time will be recorded to the closest hour.
- If no value can be obtained for all other times for events and assessments occurring after randomization, the time will not be imputed but will remain missing.
- The severity and causality assessment for adverse events cannot be missing. Missing data will be queried for a value.

For clinical and microbiological response, missing data will be handled as follows:

- For the primary outcome measure (Early Clinical Response at 72 to 120 hours after administration of the first dose of test article):
 - The subject will be considered to have missing data if an assessment of all of the CABP symptoms (cough, sputum production, pleuritic chest pain, and dyspnea) is not made from 72 to 120 hours after the administration of the first dose of test article, unless the subject is considered a Clinical Failure for another reason. Subjects who do not have at least 2 symptoms of CABP at baseline will also be considered to have missing data unless the subject is considered a Clinical Failure for another reason. Subjects with missing data will be defined as an Indeterminate response which is essentially a Clinical Failure for the primary analysis in the ITT population.
 - If the time of administration of the first dose of test article is missing, the subject will be defined as an Indeterminate response (unless the subject is considered a Clinical Failure for another reason) which is essentially a Clinical Failure for the primary analysis in the ITT population.
- For the secondary outcome measures (investigator's assessment of Clinical Response at the EOT and PTE Visits):
 - Subjects will be defined as an Indeterminate if the investigator cannot determine whether the subject is a Clinical Success or Failure at the EOT or PTE Visits or the subject has a missing response (see [Table 1](#)). By definition, subjects with an Indeterminate response are included in the denominator for analyses in the ITT and

microITT populations, and thus, are considered Clinical Failures. Subjects with an Indeterminate response are excluded from the CE-EOT, CE-PTE, ME-EOT and ME-PTE populations.

- For microbiologic response:
 - If no post-baseline source specimen is obtained and the subject has an investigator’s assessment of Clinical Response, the per-pathogen microbiological response is based on the investigator’s assessment of Clinical Response (ie, the response is a presumed response). A per-pathogen microbiological response at the EOT Visit or PTE Visit will be considered Indeterminate only if the Clinical Response at EOT or PTE is also Indeterminate.
- Missing values for other individual data points will remain as missing. Missing values will not be imputed and only observed values will be used in data analyses and presentations.
- Where individual data points are missing, categorical data will be summarized based on reduced denominators (ie, only subjects with available data will be included in the denominators).

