6.1.4.2 Prior Antibiotic Therapy

Subjects will be excluded from the CE populations if they meet the prior antibiotic exclusion criteria:

Exclusion Criterion 1: Has received 1 or more dose(s) of a potentially effective systemic antibacterial treatment within the 72 hours prior to the first dose of test article (a subject will be considered to have received a potentially effective systemic antibacterial treatment if the pathogen identified as causing infection is shown to be susceptible to the antibacterial given or, in the circumstance where a pathogen is not identified, if the antibacterial agent is approved for treatment of pneumonia or is known to have activity against any of the leading

causes of CABP [eg, *Streptococcus pneumoniae*, *Haemophilus influenzae*, *Moraxella catarrhalis*, *Staphylococcus aureus*, *Legionella pneumophila*]. EXCEPTION: Subjects may be eligible despite prior antibacterial therapy if they have been treated with a single dose of a short-acting antibacterial (ie, an antibacterial whose standard dosing regimen is more frequent than once per day, see [Appendix 1](#) of the protocol). Enrollment of subjects who received a single dose of an allowed short-acting antibiotic within the 72 hours prior to the first dose of test article will be limited to no more than 25% of randomized subjects.

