13.2 Prior and Concomitant Medications

All medications taken within 7 days prior to the date of informed consent through the Final Follow-up Visit will be recorded on the eCRF. Prior medications will be summarized by WHODRUG (Version 01 Dec 2014) Anatomical Therapeutic Chemical Classification (ATC) level 3 (third level indicates the therapeutic/pharmacologic subgroup) and generic medication name. Medications are considered prior if taken prior to the first infusion of test article or if their start date is unknown. Subjects will be counted only once for an ATC class and generic medication name. Concomitant medications taken during and after the study treatment period will be similarly summarized. Medications are considered concomitant if taken on or after the first infusion of test article, or if their stop date is unknown or marked as continuing.

The number and percentage of subjects who receive the following prior and concomitant medications will be summarized by treatment group:

- Systemic antibacterial medications taken within 72 hours prior to first infusion of test article and the reasons for receipt (ITT and CE-PTE populations)
- Systemic antibacterial medications (excluding test article) taken between first infusion of test article and the EOT Visit (CE-EOT population) and the reasons for receipt
- Systemic antibacterial medications (excluding test article) taken between first infusion of test article and the PTE Visit (CE-PTE population) and the reasons for receipt
- Non-antibacterial medications taken prior to informed consent through the first infusion of test article (ITT and Safety populations)
- Non-antibacterial medications taken from the first infusion of test article through the Final Follow-up Visit (ITT and Safety populations)

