Stop date for con meds	Non-Antibacterial	If it cannot be determined whether or not the stop date of a medication (^{nonantibacterial}) is after the first dose of study drug, it will be assumed that the medication was received after the first dose of study drug
	Antibacterial	Missing stop dates for antibacterials will be queried for a value. If it cannot be determined whether or not the stop date of an antibacterial is after the first dose of study drug, it will be assumed that the medication was received after the first dose of study drug unless the indication notes that the medication was received prior to the first dose of study drug. If it cannot be determined whether the antibacterial was received prior to the assessment of Early Clinical Response, the EOT and/or the PTE Visit, the antibacterial will be assumed to have been received through the PTE Visit.

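### Setting a missing prior-antibiotic time to 00:01 puts essentially every dose dated three days before first dose outside the 72-hour look-back used for the CE populations

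*Combined protocol and SAP*

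**What the plan says.** SAP 8.3 starts with a query: "Missing start and stop times for prior and concomitant antibiotics will be queried for a value". If the query fails and the site states that "the antibiotic was received (onset time) prior to the first dose of test article, 00:01 will be used for the onset time", the onset time is filled in. The end time is handled separately: "00:01 will be used for end time" only where the site also confirms that the end preceded first dose.

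SAP 6.1.4.2 applies protocol Exclusion Criterion 1 to the evaluable sets: "Subjects will be excluded from the CE populations if they meet the prior antibiotic exclusion criteria". The criterion is "Has received 1 or more dose(s) of a potentially effective systemic antibacterial treatment within the 72 hours prior to the first dose of test article", with an exception for a single dose of a short-acting agent. SAP 6.1.5 builds the ME populations from the CE populations, so they inherit the exclusion. SAP 13.2 also tabulates "Systemic antibacterial medications taken within 72 hours prior to first infusion of test article", for ITT and CE-PTE.

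Under SAP 6.2.2, CE membership comes from a program run on eCRF data plus manual review by the blinded Evaluability Review Team. Neither that section nor any other gives a different clock time for the 72-hour check.

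**The concern.** The look-back is counted in hours from first dose, so for a dose dated exactly three days earlier the clock time alone decides whether it is inside. The imputation picks the earliest minute of that date, which is the choice least likely to count the dose. A subject who had a disallowed antibacterial inside 72 hours can therefore stay in CE-EOT, CE-PTE and the ME sets, contrary to the definition of those populations, and be missed in the SAP 13.2 table.

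Keeping pretreated subjects in an evaluable set could blunt a difference between arms, which is the unhelpful direction in a non-inferiority comparison. That is a statistical inference. The protocol states the exclusion without giving a reason for it.

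**Working it through.** The plan gives no figure on this point to reproduce. The check is clock arithmetic.

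**Inputs.** Imputed time 00:01 (SAP 8.3). Window of 72 h back from first dose (SAP 6.1.4.2), with exactly 72 h counted as inside. First dose on date D at clock time T. Antibiotic dated D−k.

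**Elapsed time under the rule** = 24k h + T − 1 min.

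- k = 0, 1 or 2: the true gap is always under 72 h (at most 48 h + 23 h 59 min = 71 h 59 min for k = 2). Status does not depend on the time.
- k = 4 or more: the true gap is always over 72 h (at least 72 h 1 min, from 23:59 on D−4 to 00:00 on D). Status does not depend on the time.
- k = 3: the imputed gap is 72 h + T − 1 min. It exceeds 72 h for every T after 00:01, which is 1438 of 1440 minutes. The exceptions are 00:00 (71 h 59 min) and 00:01 (exactly 72 h).

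**True status for k = 3.** A D−3 dose is inside the window if it was given at or after clock time T. If dose times are uniform over the day (assumption), the share truly inside is (24 − T)/24 and the share truly outside is T/24.

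| First dose (T) | Gap under 00:01 | Truly inside, called outside | Truly outside |
|---|---|---|---|
| 08:00 | 79 h 59 min | 16/24 = 67% | 8/24 = 33% |
| 10:00 | 81 h 59 min | 14/24 = 58% | 10/24 = 42% |
| 14:00 | 85 h 59 min | 10/24 = 42% | 14/24 = 58% |
| 20:00 | 91 h 59 min | 4/24 = 17% | 20/24 = 83% |

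Enumerating every pair of minutes for k = 3, 49.9% of cases move from truly inside to called outside, and 0% move the other way.

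**Example.** Ceftriaxone is in the disallowed column of protocol Appendix 1. Given at 20:00 on D−3 with first dose at 10:00 on D, the true gap is 62 h and the exclusion applies. With the time missing, the gap becomes 81 h 59 min and it does not.

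**Check of the alternative.** With 23:59 on D−3 the gap is 48 h 1 min + T, at most 72 h, so the dose is inside for all 1440 first-dose minutes. D−4 and earlier stay outside; D−1 and D−2 stay inside.

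**The case against.** **Reach.** A subject is wrongly kept only if the last non-exempt dose was on D−3, the time stayed missing after a query, and the true time was later than the first-dose clock time. The site must also have passed the subject as eligible, and the Evaluability Review Team must have left the subject in after blinded review. This stands: the documents give no rate of missing times, and the number is probably very small. It does not remove the point, because the review team has no written rule for such a case and would not know the true time either.

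**No formal test in this SAP is affected.** Also right. Non-inferiority and superiority are tested on Early Clinical Response in ITT (SAP 10.1, 10.2), and SAP 10.3 makes the CE-PTE and ME-PTE intervals descriptive. A reader might infer that the EMA co-primary analysis in CE is compromised. The documents do not support that: it has its own SAP, which is not among them, so the effect is conditional on that SAP using the same rule.

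**The 25% cap.** A reader might think the cap on allowed prior antibiotics is weakened. It is not: the IxRS applies it at randomization, before any imputation.

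**Appendix 3.** A reader might see a contradiction with the rule that "the antibacterial will be assumed to have been received through the PTE Visit". The comparison is loose. Appendix 3 imputes dates, and that sentence concerns timing relative to the response assessments. For unclear antibacterial start dates it generally assumes receipt before first dose, which agrees with what 00:01 is meant to do.

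**Symmetry.** The alternative misclassifies the complementary share: 33%, 42%, 58% or 83% for the four first-dose times, which is worse than 00:01 in two of them and about equal averaged over the day. The arithmetic stands, but the two errors do not cost the same. Dropping a subject on a baseline record loses a little CE size. Keeping one who had non-exempt therapy inside 72 hours breaks the definition of the set.

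**Conclusion.** The point holds as a minor data-handling defect. For the 72-hour check, the 00:01 rule classes a D−3 dose of unknown time as outside for every first-dose time except 00:00 and 00:01, and its errors run in one direction only. The shares truly inside (67%, 58%, 42% and 17% at the four times shown) rest on uniform dose times, which the documents neither state nor contradict. The number of subjects cannot be computed from the documents.

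The exposed outputs are the descriptive CE-EOT, CE-PTE and ME analyses and the SAP 13.2 table of antibacterials within 72 hours. The FDA primary conclusion does not depend on this rule. The case for changing it is that the correction is cheap.

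**What to change.** In SAP 8.3, keep 00:01 for ordering antibiotics dated on the day of first dose. Add one sentence: for the 72-hour look-back only (SAP 6.1.4.2 and the SAP 13.2 table), a missing onset or end time that the site confirms was before first dose is set to the latest time compatible with the record. That is 23:59 on an earlier date, or just before first dose on the same date. Doses of undetermined timing then count as inside the window. The EMA SAP should be checked for the same rule.

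The cost is that sentence and a small program change, plus the possible loss from CE of subjects whose D−3 dose was truly outside 72 hours (the last column of the table above). Given the expected numbers, the loss of CE size should be small.
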